4.5. Study procedure

The study to be conducted will be single-blinded, randomized controlled, parallel design. The study population will consist of Seventy-two (72) male and female subjects conforming to the following admission criteria. The subjects meeting the admission criteria with an anticipation of 40% dropout rate will be stratified into two groups balanced for MGI, BOP, PI, and gender using screening data. In this single-blind design, product assignment will be randomized after screening, and only the PI and the Study coordinator will have access to the randomization key.

One group will be assigned to a new power toothbrush while the control group will be assigned an ADA approved manual toothbrush. The study involves a 12-week home use of the respective toothbrushes. Both groups will refrain from the regular use of mouthwash and any interdental device, such as floss, floss picks, toothpicks, water flossing device or interdental brush, during the length of the study. Written instructions on brushing and professional brushing demonstration will be provided at the outset of the study and each participant from both test and control groups will also receive a 2-minute timer to help them monitor their brushing time. Before each visit, subjects are expected to have at least 7 hours, but no more than 12 hours of accumulated, non-brushed, undisturbed plaque/debris.

The study includes four or five visits – screening, baseline, 2-week follow-up, 4-week follow-up and 12-week follow-up. Schematic 1 summarizes the study procedure and visits and Table 2 details procedures in this study. The Screening and the baseline visit may happen on the same day.

Schematic 1. Study and visit procedures

CONFIDENTIAL

CONFIDENTIAL

Visit 2: Baseline
(continued)

A

Use brush per instruction

PI examination after
brushing

Single use
result

Schedule next visit

Pre visit

7 – 12 hours of plaque
accumulation

Visit 3: Follow-up visit
at 2 weeks

Oral examination for tissue abrasion and MGI
by calibrated examiners

Periodontal probing for BOP and PPD
by calibrated examiners

Oral examination for PI
By calibrated examiners

Schedule next visit

Pre visit

7 – 12 hours of plaque
accumulation

Visit 4: Follow-up visit
at 4 weeks

[figure not shown]
Oral examination for tissue abrasion and MGI
by calibrated examiners

Periodontal probing for BOP and PPD
by calibrated examiners

Oral examination for PI
by calibrated examiner

Schedule next visit

A

CONFIDENTIAL

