The first follow-up will take place two weeks after the baseline visit. Subjects can schedule the visit for any time between two days before and after the two-week use period (12-16 day range). Clinical examinations will be given to the subjects in the same order as the baseline visit with the exception that no second plaque index will be recorded. All subjects must present with 7 to 12 hours of undisturbed plaque. The oral safety exam will include a thorough examination of the gingiva to look for any signs of gingival trauma, irritation or abrasion. Any subjects who show signs of gingival trauma that appears to be toothbrush related will be exited from the study. The recorded findings will be reported as Adverse Events. In addition, any site in the mouth that shows an increase in probing pocket depth of 2 mm or greater from the baseline measurement will have that particular site treated with subgingival scaling and root planing or whatever the PI deems appropriate therapy. If subjects meet any of the discontinuation criteria, they will be withdrawn from the study.

Visit 4: Four-week follow-up

This visit should take place four weeks after the baseline visit within three days before and after the four week mark (25-31 day range). Subjects will receive full mouth examinations in the same order as the previous visit. Additionally, inspection for signs of gingival trauma and increase in PPD greater than 2 mm from the baseline will be conducted and evaluated. The PI will determine if any subject meets the discontinuation criteria as well as appropriate therapy to treat.

Visit 5: 12-week follow-up

In this visit, subjects will return the products, including manual toothbrush, or brush head, brush handle, and charger. The procedure is similar to the four-week follow-up visit, in which full mouth clinical examination will be carried out as before on each of the subjects. The subjects' disclosed plaque will be evaluated as usual. The examined results will be recorded. Prophylaxis will be carried out as needed.

The used brushes/brush heads will be returned to sponsor at the end of the trial and examined for wear as an additional measure of compliance.

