5.3. Discontinuation criteria

The oral safety exam at the follow-up visits will include a thorough examination of the gingiva to look for any signs of gingival trauma, irritation or abrasion, as well as a periodontal probing. Any subjects who show signs of gingival trauma that appears to be toothbrush related will be exited from the study and the findings reported as Adverse Events. In addition, subjects may be discontinued due to the following reasons.

1. Voluntary discontinuation: subjects are free to discontinue their participation in the study at any time.
2. Safety concerns: the principal investigator may terminate a subject's participation if gingival trauma occurs and appears to be toothbrush related
3. Significant non-compliance to protocol: the principal investigator may terminate a subject's participation if subjects are shown to be non-compliant to the protocol
4. Incorrect enrollment: subjects who did not meet admission/exclusion criteria
5. Subject received any type of dental treatment/care other than those required in the study, for example use of interdental devices, mouthrinses, chewing gum or prophylaxis treatment, without consent of the investigator

Subjects who discontinue should be asked to a follow-up visit to observe any Adverse Events.

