7. STATISTICAL ANALYSIS

Each of the two research groups' patients will be assessed clinically at four time points (Baseline, 2 weeks, 4 weeks and 12 weeks). These measures will be compared against one another and over time using a between-within factors repeated measures ANOVA.

Further evaluation of interproximal and marginal scores will also be evaluated with a post hoc analysis.

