7.1. Sample size

Assuming an alpha/p-value of 0.05, and a power of 0.95, the minimum number of subjects needed (after all drop-outs have been removed) is 44. Due to the length of the study and multiple visits required within the length of the study, the potential for moderately high drop-out rates is set at 40%. 72 subjects will be initially enrolled; 36 will be assigned to the power toothbrush group, and 36 will be assigned to the manual toothbrush group.

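### Randomized subjects can be removed for significant non-compliance or other oral care by an investigator who has access to the randomization key, with no 12-week scoring planned afterwards, so the BOP/MGI comparison could be biased by an unknown and possibly zero amount.

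*Combined protocol and SAP*

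**What the plan says.** Section 5.3 lists grounds for discontinuation after enrolment. Item 3 covers significant non-compliance: "the principal investigator may terminate a subject's participation if subjects are shown to be non-compliant to the protocol". No threshold for significant is given. Item 5 covers dental treatment or care outside the study, "for example use of interdental devices, mouthrinses, chewing gum or prophylaxis treatment, without consent of the investigator".

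Section 4.5 describes how the criteria are applied. For Visit 3 it says: "If subjects meet any of the discontinuation criteria, they will be withdrawn from the study". For Visit 4 it says: "The PI will determine if any subject meets the discontinuation criteria as well as appropriate therapy to treat". PI also abbreviates Plaque Index in this document, but here it can only mean the principal investigator. The same section says that "only the PI and the Study coordinator will have access to the randomization key".

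On what follows discontinuation, Section 5.3 says: "Subjects who discontinue should be asked to a follow-up visit to observe any Adverse Events". It mentions no efficacy scoring.

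Section 4.3 makes the change in BOP and MGI from baseline to 12 weeks the primary endpoint. Section 7 says that the measures will be "compared against one another and over time using a between-within factors repeated measures ANOVA". It names no analysis set, missing-data rule or sensitivity analysis. Section 7.1 says that "the minimum number of subjects needed (after all drop-outs have been removed) is 44".

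**The concern.** The grounds in items 3 and 5 are plausibly related to outcome. Floss, rinses and prophylaxis are restricted because they could affect gingivitis, and poor compliance with brushing could too. Compliance may also differ by arm, because Section 5.1 admits routine manual brush users and half of them receive a power brush. The person who judges whether a criterion is met can know the arm.

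If the subjects removed differ in outcome from those who stay, and removal is not balanced between arms, the groups compared at 12 weeks differ for a reason other than the brush. Blinded examiners do not prevent this. Blinding protects the score given to a subject, not the decision on whether that subject is still there to be scored. With no 12-week scores for those removed, the effect could not be checked afterwards. The plan also allows for 40% drop-out, so such removals would be hard to tell from ordinary loss.

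**Working it through.** **The plan's own figures.** Section 7.1 gives 44 evaluable subjects, 40% drop-out and 72 enrolled (36 per arm). 44/(1 − 0.40) = 73.3, or 74 with equal arms, and 72 × 0.60 = 43.2. The stated 72 agrees to within two subjects. The 44 itself cannot be reproduced, because no effect size or SD is given.

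**Inputs from the documents.** Significance level 0.05 (Section 7.3); two-sided alternative (Section 7.4); 36 randomized per arm and 44/2 = 22 evaluable per arm (Section 7.1).

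**Assumptions, not from the documents.** A net k = 2, 4 or 7 of 36 subjects are removed selectively from one arm. Their 12-week change differs from the rest of that arm by g = 0.5 or 1 SD. All other drop-out is random, and there is no true brush effect. A two-sample t test stands in for the planned ANOVA.

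**Step 1: shift of the arm mean.** Shift = (k/36) × g. For example, k = 4 and g = 1 give 4/36 = 0.111 SD.

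**Step 2: type I error.** This is the two-sided rejection probability under a noncentral t distribution with noncentrality shift/√(1/n₁ + 1/n₂). For k = 4, g = 1 and 22 per arm it is 0.111/√(2/22) = 0.37, on 42 degrees of freedom.

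| k | g (SD) | Shift (SD) | Type I error, 22 vs 22 | Type I error, (36 − k) vs 36 |
|---|---|---|---|---|
| 2 | 0.5 | 0.028 | 5.1% | 5.2% |
| 2 | 1 | 0.056 | 5.4% | 5.6% |
| 4 | 0.5 | 0.056 | 5.4% | 5.6% |
| 4 | 1 | 0.111 | 6.5% | 7.4% |
| 7 | 0.5 | 0.097 | 6.2% | 6.7% |
| 7 | 1 | 0.194 | 9.7% | 12.0% |

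With g = 0 the error is 5.0% throughout. Equal removals with the same gap in both arms cancel.

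**Step 3: cost of keeping these subjects.** With 22 per arm, 95% power corresponds to a difference of 1.113 SD under the same t test. If k non-compliant subjects per arm are kept on top of 22 and lose a fraction L of the effect, the average effect is 1.113 × (1 − L × k/(22 + k)), with 22 + k per arm.

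| k per arm | Effect, L = 0.5 | Power | Effect, L = 1 | Power |
|---|---|---|---|---|
| 2 | 1.066 SD | 95.1% | 1.020 SD | 93.3% |
| 4 | 1.027 SD | 95.3% | 0.942 SD | 91.4% |
| 7 | 0.978 SD | 95.6% | 0.844 SD | 88.5% |

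**Step 4: a less favourable retention case.** Suppose that 7 extra users of other products are kept in the manual arm only, and that they improve by a further 1 SD. The difference falls by 7/29 = 0.241 to 0.871 SD. With 22 against 29 subjects, power is about 86%.

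**The case against.** The strongest case against the point has five parts.

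- **The bias is small in most scenarios.** Five of the six cases at 22 per arm lie between 5.1% and 6.5%. Only 7 one-sided removals with a full 1 SD gap reach 9.7%. This stands. A reader might take the 40% drop-out as a guide to how many would be removed, but Section 7.1 attributes it to the length of the study and the number of visits.
- **The criteria have limits.** Item 3 concerns significant non-compliance that has been shown, and item 5 needs a concrete event. The Visit 3 sentence makes withdrawal mandatory once a criterion is met, which narrows discretion. This stands in part. What counts as significant, and whether consent is given, remain open to judgement, and Section 5.3 itself is permissive where Visit 3 is mandatory.
- **Removal protects a brush-only comparison.** Section 5.1 has subjects agree to use the assigned brush alone. That question is legitimate, and a sensitivity analysis can address it without losing the outcome data.
- **Retention has its own cost.** Steps 3 and 4 above show that power can fall below the planned 95%. This stands, although in those cases the shift runs towards no difference.
- **A lighter remedy exists.** Someone blind to arm could judge deviations. That would remove knowledge of the arm from the decision, but the 12-week scores would still be missing.

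Two stronger readings are tempting. One is that the investigator will remove subjects according to arm; nothing in the documents shows this. The other is that the plan prescribes a completers-only analysis. The sample-size wording points that way, but Section 7 names no analysis set, so this is an inference.

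**Conclusion.** The point holds as a possible bias, not a demonstrated one. Three stated features combine: removal after randomization on grounds that may relate to outcome, a decision by someone with access to the key, and no efficacy scoring afterwards. Nothing in Section 7 offsets them.

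The size cannot be computed from the documents and may be zero. Under the assumed one-sided removals, the arm mean shifts by 0.03 to 0.19 SD. Type I error is 5.1% to 9.7% at 22 per arm, and 5.2% to 12.0% with little other drop-out. With up to 4 removed it is at most 6.5% and 7.4% respectively. The change is worth making because it is cheap and removes the dependence on discretion, not because a large error has been shown.

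The differing wording on rinses and interdental cleaning in Sections 4.5, 5.1 (item 3) and 5.3 (item 5) is a separate clerical matter and does not cause the bias.

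**What to change.** - In Section 5.3, items 3 and 5, and in the matching withdrawal sentences for Visits 3 and 4 in Section 4.5, record non-compliance and use of other oral care, including prophylaxis, as protocol deviations and not as grounds for removal from follow-up.
- Score BOP and MGI at the existing 12-week visit for every randomized subject willing to attend. This includes subjects who stop the assigned brush because of toothbrush-related trauma and those found to have been enrolled incorrectly. Subjects with such trauma still stop the brush for safety, and voluntary withdrawal is unchanged.
- State in Section 7 that all are analysed in the arm to which they were randomized, with one sensitivity analysis excluding subjects with significant deviations. Significance is best judged by someone without access to the key.
- As a clerical edit, align the rinse and interdental wording across the three sections.

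The cost is a small amendment and one extra analysis, with no new visit or staff and no change to the 72 enrolled. The downside is dilution. If 2 to 7 non-compliant subjects per arm are kept on top of 22, power is about 95% if they get half the effect and 88% to 93% if they get none. It is about 86% if 7 extra product users in the manual arm alone improve by a further 1 SD.

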4.3. Primary endpoint

The primary endpoint of this study is reduction of gingivitis (change from baseline) as measured by BOP and MGI at baseline, and again at 12-week visits.

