7.4. Method

Reductions in gingivitis – BOP, MGI and PPD – and plaque – PI from baseline scores after 2 weeks, 4 weeks and 12 weeks of use will be evaluated. For each subject, mean score of each index will be calculated as well as reductions from baseline at three time points. Additionally, numbers of abrasion sites found will be compared.

Assuming evaluated scores for the test and control groups are denoted U_{Test} and U_{Control} , respectively, the null hypothesis will be tested.

$$H_0: U_{\text{Test}} - U_{\text{Control}} = 0$$

$$H_1: U_{\text{Test}} - U_{\text{Control}} \neq 0$$

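### Discontinuation is treated as leaving the study and only an adverse-event visit is planned afterwards, so no week-12 BOP or MGI is planned for these subjects and the primary comparison can be biased

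*Combined protocol and SAP*

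**What the plan says.** The primary endpoint in Section 4.3 is "reduction of gingivitis (change from baseline) as measured by BOP and MGI at baseline, and again at 12-week visits". A subject without a week-12 score has no primary outcome.

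Three places determine what happens to a subject who discontinues:

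- Section 5.3, opening text: "Any subjects who show signs of gingival trauma that appears to be toothbrush related will be exited from the study". The numbered list adds voluntary discontinuation, non-compliance, incorrect enrolment and dental care outside the study. On non-compliance it says that "the principal investigator may terminate a subject's participation if subjects are shown to be non-compliant to the protocol".
- Section 4.5, Visit 3: "If subjects meet any of the discontinuation criteria, they will be withdrawn from the study".
- Section 5.3, closing sentence: "Subjects who discontinue should be asked to a follow-up visit to observe any Adverse Events". It gives no timing and names no index.

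Neither Table 2 nor the Patient Schedule at the end of the document has an early-termination visit or a later visit for discontinued subjects. Section 7 names no analysis set and no method for missing scores. It specifies a between-within repeated measures ANOVA. Section 7.1 states the required 44 subjects as a count that excludes drop-outs, and adds that "the potential for moderately high drop-out rates is set at 40" per cent.

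**The concern.** Stopping the assigned brush and leaving the study are two different events, and the plan merges them. Brush-related trauma, non-compliance, incorrect enrolment and outside dental care do not in themselves prevent a subject from attending week 12. Under the plan as written, the outcome is still not sought.

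These exits occur after randomisation and can depend on the arm. Trauma attributed to the brush depends on the product under test. Subjects know which brush they have. Outside care, such as interdental devices or mouthrinse, can itself affect gingivitis. Termination for non-compliance is left to the principal investigator, who under Section 4.5 has access to the randomisation key. A person able to know the assignment can thus decide who leaves, and no later outcome is then planned for that subject.

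What is at stake is the randomised comparison on the primary endpoint. An analysis section can be amended later, but week-12 scores that were not taken cannot be recovered.

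**Working it through.** **Inputs from the documents.** 72 enrolled, 36 per arm; 44 needed after drop-out; drop-out 40% (all Section 7.1); significance level 0.05 (Section 7.3), with a two-sided alternative (Section 7.4).

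**The plan's own figure.** 44 / (1 − 0.40) = 73.3, or 74 when rounded up to an even number. The stated 72 is within two subjects of this. In the other direction, 72 × 0.40 = 28.8 leavers and 72 × 0.60 = 43.2 completers, just under 44. The plan therefore allows for up to about 29 subjects without a week-12 score. It does not say how many of these would be investigator-initiated exits.

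**Bias of a completers-only comparison.** Let m be the share of an arm without a week-12 score. Let g be the amount, in SD units, by which leavers in that arm improve less than its completers. The completers' mean exceeds the mean of the whole arm by m × g, so

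bias = mT × gT − mC × gC (T = power, C = manual).

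The documents give no value for m by arm or for g. All values below are assumptions.

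*Same deficit g in both arms.* The formula reduces to (mT − mC) × g:

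- 10-point difference, g = 0.5: 0.10 × 0.5 = 0.05 SD
- 20-point difference, g = 1.0: 0.20 × 1.0 = 0.20 SD

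*Equal drop-out of 40% in both arms:*

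- g = 0.5 in both: 0.40 × 0.5 − 0.40 × 0.5 = 0
- g = 1.0 and 0.5: 0.40 − 0.20 = 0.20 SD
- g = 1.0 and 0: 0.40 − 0 = 0.40 SD

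*Lower loss, 10% in each arm:* the same three pairs of g give 0, 0.05 and 0.10 SD.

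Equal drop-out rates therefore do not protect the comparison by themselves. The sign follows the arm with the larger m × g. Heavier selective loss from the power arm flatters the power brush, and heavier loss from the manual arm does the opposite.

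**Effect on the type I error.** Suppose there is no true difference among all randomised subjects. With 40% missing per arm, 36 × 0.60 = 21.6 remain in each arm, and the standard error is √(1/21.6 + 1/21.6) = 0.304 SD. The two-sided error is 1 − Φ(1.96 − b/0.304) + Φ(−1.96 − b/0.304):

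- b = 0.20: about 0.10
- b = 0.40: about 0.26

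With 40% and 20% missing and g = 0.5 in both arms, b = 0.10 and the error is about 0.064.

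**The case against.** **The gap is silence, not a prohibition.** Section 5.3 states the purpose of the later visit and excludes no examination. This stands. A reader might infer that scores are never collected after discontinuation. The documents support only that none are planned. A subject exited at the week-12 visit itself may still have week-12 scores.

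**Exit is not always mandatory.** Termination for non-compliance is discretionary, so some non-compliers may stay. A reader might infer that the comparison rests only on subjects who tolerated and complied with their brush. On compliance, that goes too far.

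**Scores at the exit visit.** Because trauma is examined first, one might infer that a subject exited at that step loses that visit's MGI and BOP. The text does not support this. Section 5.3 includes probing in the safety exam, BOP is recorded after probing (Section 4.2.5), and the Patient Schedule has the same first examiners do the oral exam, MGI, probing and BOP.

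**Precision.** Recovering some leavers might seem to bring a clear gain in precision. If a quarter to a half of the 28.8 returned (an assumption), the number analysed would be 50.4 to 57.6. The standard error would fall by 7 to 13%, since √(43.2/50.4) = 0.926 and √(43.2/57.6) = 0.866. But Section 7.1 attributes the 40% to study length and number of visits, which suggests people who stop attending. Entrants are also routine manual-brush users. If those retrieved kept none of the effect, the contrast would shrink by 7.2/50.4 = 14% to 14.4/57.6 = 25%. The ratio of signal to noise would then be 0.857/0.926 = 0.93 to 0.75/0.866 = 0.87 of its former value. Break-even needs about half the effect to be kept. No precision gain is claimed.

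**Analysis could help.** A reader might infer that no method can repair the loss. That is too absolute. Baseline and any week-2 and week-4 scores support a likelihood-based analysis under missing at random, with sensitivity analyses. These would still rest on assumptions about unobserved scores that cannot be tested.

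**Few trauma exits are expected.** Section 2.2 cites a review that found no apparent link between power brushes and soft tissue trauma. This is fair, and it is one reason why the arm differences above are illustrations and not predictions.

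**Choice of estimand.** Scoring subjects after they stop, in their assigned arm, answers a treatment-policy question, and the plan names no estimand. This stands, and it is why an on-brush analysis should be kept alongside.

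**Conclusion.** The point holds in this form: discontinuation means leaving the study, only a safety visit is planned afterwards, and no week-12 BOP or MGI is planned for these subjects. The reasons for exit arise after randomisation and may depend on the arm, so the primary comparison can be biased.

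The completers-only reading comes from the way Section 7.1 counts subjects and from the classical form of the ANOVA, which uses only subjects with all four time points. It does not come from a stated analysis set.

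The size and direction cannot be derived from the documents. The illustrative 0.05 to 0.20 SD assumes a 10 to 20 point arm difference and a common deficit of 0.5 to 1.0 SD. Other assumptions give zero, a larger bias or the opposite sign. The case for change is that collecting these outcomes is cheap and can reduce the bias.

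**What to change.** In Section 5.3 and the Visit 3 and Visit 4 text, leave decisions to stop brush use or to treat as they are, and separate them from outcome collection:

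1. State that discontinued subjects who have not withdrawn consent, and for whom the investigator sees no safety objection, are invited to the remaining scheduled visits, at least week 12, for MGI, BOP and plaque scoring by the blinded examiners.
2. Record the date and reason for discontinuation, the brush used afterwards and any dental care received.
3. In Section 7, analyse these scores in the assigned arm, with an on-brush analysis as a sensitivity analysis.

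Separately, the sponsor must reconcile two conflicts. For brush-related trauma, the opening of Section 5.3 makes exit mandatory while item 2 of its list makes it discretionary. For the listed reasons generally, Section 5.3 permits discontinuation while the Visit 3 text requires withdrawal. This review does not say which reading is right.

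Cost: protocol wording and a line in the consent form. The visits, the examiners and the $25 reimbursement (Section 11) already exist, and Section 5.2 already excludes people who cannot commit to all visits through week 12. Downsides: time off the assigned brush may dilute the contrast, and some subjects will decline.
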